6.3 Duration of Study

6.3.1 Duration of an Individual Patient's Study Participation

Patients may receive modakafusp alfa as a SA for up to 1 year or in combination with pembrolizumab for up to 2 years. Patients with demonstrated clinical benefit can continue treatment beyond those points if approved by the sponsor. These patients can continue receiving treatment in this study or in any of the poststudy access modalities described in the protocol (Section 6.3.5). Patients may discontinue treatment when they meet any of the discontinuation criteria stated in the protocol (Section 9.6).

All patients will have an EOT visit 30 days (+10 days) after receiving the last dose of study drug or before the start of subsequent systemic anticancer therapy, whichever occurs first, to permit detection of any delayed TEAEs and to resolve any ongoing events. Patients with unresolved TEAEs will continue the periodic safety follow-up until complete resolution or stabilization (established as sequelae) occurs.

Patients who discontinue study treatment for reasons other than progressive disease (PD) will continue PFS follow-up every 12 ± 1 weeks from the EOT visit until the occurrence of PD, lost to follow-up, consent withdrawal, death, start of subsequent systemic anticancer therapy, or study termination, whichever occurs first. After disease progression or starting another systemic anticancer therapy, all patients will be followed every 12 ± 1 weeks for OS until death or study termination.

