- ^f CT and/or MRI scans of the chest, abdominal cavity, and pelvis should be acquired with at least IV contrast. The imaging modalities used for a patient should remain consistent throughout the study. If IV contrast-enhanced CT scans are contraindicated for a particular patient, a noncontrast-enhanced CT of the chest should be acquired in addition to an oral contrast-enhanced CT of the abdomen and IV contrast-enhanced pelvic MRI. At present, low-dose or attenuation correction CT portions of a combined PET-CT are of limited use in anatomically based efficacy assessments, and it is therefore suggested that they should not be substituted for dedicated diagnostic contrast-enhanced CT scans for anatomically based RECIST measurements. However, if a site can document that the CT performed as part of a PET-CT is of identical diagnostic quality to a diagnostic CT (with IV and oral contrast), then the CT portion of the PET-CT can be used for RECIST measurements. Note, however, that the PET portion of the CT introduces additional data that may bias an investigator if it is not routinely or serially performed. Repeat CT and/or MRI scans should be performed every other cycle up to Cycle 7 (Day 1 [-7 days] of Cycles 3, 5, and 7), every 3 cycles thereafter, and as clinically indicated. Response will be determined locally according to RECIST v1.1 (see Section [9.3.14.1](#)). Screening and on-treatment images, when available, should be submitted to the imaging core laboratory vendor for retrospective central reading when it is required. Clinical decisions will be made per local response assessment. Availability of prescreening scan(s) is not a prerequisite for study eligibility (Section [9.3.14.2](#)). If available, the most recent prescreening diagnostic quality CT and/or MRI scans dated within 3 months before the planned first dose of modakafusp alfa should be submitted to the imaging core laboratory vendor for tumor growth rate determination. The date of the scan should be indicated. Response assessment will be calendar-based regardless of treatment delays/interruptions.

- ^g Chemistry will include tests listed in [Table 9.a](#). Chemistry on C1D15 and C3D15 could be assessed in a local hospital if there is no planned PK sampling on those visits per [Table 16.g](#) and [Table 16.h](#).

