7.9 Efficacy Analysis

Response will be assessed according to mRECIST 1.1 for all patients. Response will also be assessed according to iRECIST for patients in Phase 2 expansion cohort.

Best Overall Response (BOR)

Best overall response is defined as the best response (per investigator assessment as defined by mRECIST 1.1 or iRECIST Criteria) recorded after the first dose of the study drug until a subsequent anti-cancer therapy. Response assessments after treatment discontinuation but before the initiation of a subsequent anti-cancer therapy should be included in the analysis of BOR. This will be ordered from best to worst: Complete Response (CR or iCR), Partial Response (PR or iPR), Stable Disease (SD or iSD), Progressive Disease (PD, iUPD or iCPD), Not Evaluable (NE or iNE).

Waterfall plots for best percentage change in the size of target lesions as per mRECIST 1.1 criteria will also be presented. The plot will have the following information:

1. Response,
2. Dose,
3. Cohort
4. Phase (escalation, safety lead-in or expansion).

Best overall response will be summarized and listed for all patients in the response evaluable analysis set. Overall response will be listed for all patients in the response evaluable set for each visit along with percentage change in the size of target lesions per mRECIST 1.1 criteria. If target lesion is believed to be present but too small to measure, a value of 5 mm is assigned per mRECIST 1.1.

Overall Response Rate (ORR)

The ORR is defined as the proportion of patients who have achieved the best response of CR or PR during the study per investigator assessment as defined by mRECIST 1.1 or iRECIST Criteria. The ORR will be summarized by frequencies and percentages for patients in the response evaluable analysis set. A binomial exact confidence interval will also be provided when possible.

Disease Control Rate (DCR)

The DCR is defined as the proportion of patients who have achieved the best response of CR, PR or SD during the study per investigator assessment as defined by mRECIST 1.1 or iRECIST Criteria. The DCR will be summarized by frequencies and percentages for patients in the response evaluable analysis set. A binomial exact confidence interval will also be provided when possible.

Duration of Response (DOR)

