The DOR will be tabulated for those patients with a CR or PR during the study per investigator assessment as defined by mRECIST 1.1 or iRECIST Criteria in the response evaluable analysis set with a reasonable number of responses. The DOR is defined as the number of days from the first documentation of a response until progressive disease or death, whichever occurs first. If a patient misses two consecutive disease assessments, then follow-up for the primary endpoint will be censored at the time of last non-progressive scan prior to the missed interval.

The censoring rules and censoring date in the analysis of DOR will be the same as for PFS and TTP.

$$\text{DOR (months)} = (\text{date of progression or death or censor} - \text{date of confirmed response} + 1) / 30.4375.$$

The Kaplan-Meier method will be used to estimate the distribution of DOR. The 25th, 50th (median), and 75th percentiles, and the corresponding 2-sided 95% confidence intervals (CIs) based on Brookmeyer and Crowley method (Brookmeyer and Crowley 1982), will be presented. The number of patients with events and the number of patients censored will be summarized. DOR for all patients with a response will be listed.

Progression Free Survival (PFS)

PFS is defined as the time from the date of first dose to the date of PD (or iCPD) (per investigator assessment as defined by mRECIST 1.1 or iRECIST Criteria) or the date of death due to any cause, whichever occurs first. Patients without documentation of PD (or iCPD) or death will be censored at the date of the last response assessment that is SD (iSD) or better, and prior to or on the date of initiation of alternative anti-cancer therapy if patients start new treatments. Patients with no post baseline response assessment will be censored on day 1.

$$\text{PFS (months)} = (\text{earliest date of progression or death or censor} - \text{date of first dose} + 1) / 30.4375.$$

The analysis of PFS will be based on the safety analysis set with a reasonable number of patients. The Kaplan-Meier method will be used to estimate the distribution of PFS. Kaplan-Meier survival curves, the 25th, 50th (median), and 75th percentiles, along with associated 2-sided 95% confidence intervals (CIs) based on Brookmeyer and Crowley method, and Kaplan-Meier PFS

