If *year* is missing (or completely missing): do not impute.

If (*year* is present and *month* and *day* are missing) or (*year* and *day* are present and *month* is missing):

Set *month* and *day* to December 31st.

If *year* and *month* are present and *day* is missing:

Set *day* to last day of the month.

Incomplete Subsequent Anti-Cancer Therapy Start Date

If *year* is missing (or completely missing): set to date of last dose of study treatment + 1

If (*year* is present and *month* and *day* are missing) or (*year* and *day* are present and *month* is missing):

If *year* > year of the last dose: Set *month* and *day* to January 1st.

If *year* = year of the last dose: Set *month* and *day* to date of last dose of study treatment +1.

If *year* and *month* are present and *day* is missing:

Set *day* to 1st day of month if the resulting imputed date is greater than date of last dose.

Otherwise set the imputed date to date of last dose + 1.

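### An incomplete start date for subsequent therapy is imputed without regard to scans already on record, so it can precede assessments that should count for best response and for PFS, DOR and TTP censoring

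*SAP*

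**What the plan says.** SAP Appendix B treats an incomplete start date of subsequent therapy in branches:

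- Year missing: "set to date of last dose of study treatment + 1".
- Month missing, year equal to that of the last dose: "Set *month* and *day* to date of last dose of study treatment +1".
- Month missing, later year: "If *year* > year of the last dose: Set *month* and *day* to January 1st".
- Only the day missing: "Set *day* to 1st day of month if the resulting imputed date is greater than date of last dose"; failing that, the day after the last dose.

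This date then limits the efficacy derivations in SAP 7.9. For best overall response (BOR), "Response assessments after treatment discontinuation but before the initiation of a subsequent anti-cancer therapy should be included in the analysis of BOR". For PFS, a patient without progression or death is censored at the last non-progression assessment that is "prior to or on the date of initiation of alternative anti-cancer therapy if patients start new treatments". TTP has a similar limit, and DOR takes its censoring from PFS and TTP.

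On timing, the protocol's Schedules of Events (Appendix A) ask for scans "every other cycle up to Cycle 7 (Day 1 [-7 days] of Cycles 3, 5, and 7" and then every third cycle. Protocol 6.3.1 has patients who stop for reasons other than progression followed every 12 ± 1 weeks from the end-of-treatment (EOT) visit "until the occurrence of PD, lost to follow-up, consent withdrawal, death, start of subsequent systemic anticancer therapy" or study termination. Protocol 9.7 also ends this follow-up when new systemic therapy starts.

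**The concern.** Every branch takes the earliest date that the known parts allow after the last dose, and none asks whether the patient had a study scan after that date. Because PFS follow-up ends when new therapy starts, a follow-up scan done per protocol is itself evidence that therapy had not begun. An imputed start before that scan contradicts the trial's own data, and the imputed value wins.

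BOR feeds ORR, the primary endpoint of the phase 2 expansion, and also DCR. If the scan that first shows a response is cut, the responder is lost. If it shows continued response or stable disease, event-free follow-up is cut from PFS, DOR and TTP.

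**Working it through.** The plan states no figure on this point, so there is none to reproduce. The check sets the imputation branches against the visit schedule.

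**When scans fall after the last dose.** Cycles are 21 days. A scan due on Day 1, or up to 7 days before, of the cycle after the last dose falls 21 − 7 = 14 to 21 days after that dose. Scan cycles are 3, 5, 7, 10 and so on, so this applies when the last dose is in Cycle 2, 4, 6, 9 and so on. If the last dose is in a scan cycle itself, such as C3D1, that scan comes on or before the dose and the next is due 42 − 7 = 35 to 42 days later. EOT is 30 to 40 days after the last dose. The first PFS follow-up is 12 ± 1 weeks (77 to 91 days) later, so 30 + 77 = 107 to 40 + 91 = 131 days after the last dose.

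**Illustrative patient (assumed dates).** First dose 10 Jan 2022; last dose C4D1, 14 Mar 2022 (day 64). Scans on 21 Feb (day 43), 4 Apr (day 85) and, in PFS follow-up, 6 Jul (day 178). No progression. New therapy truly starts on 16 Jul 2022. By the SAP formula, PFS in months = (censoring date − first dose + 1)/30.4375, that is, the day number divided by 30.4375.

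| Recorded start | Imputed start | Scans kept | PFS censored at |
|---|---|---|---|
| No year | 15 Mar 2022 | 1 of 3 | 43/30.4375 = 1.41 months |
| 2022 only | 15 Mar 2022 | 1 of 3 | 1.41 months |
| July 2022 | 1 Jul 2022 | 2 of 3 | 85/30.4375 = 2.79 months |
| Full date | none needed | 3 of 3 | 178/30.4375 = 5.85 months |

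The later-year branch can do the same. With the last dose on 14 Nov 2022, a follow-up scan 114 days later on 8 Mar 2023, and only 2023 recorded, the imputed start is 1 Jan 2023 and the scan is cut.

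**DOR.** Suppose this patient's partial response is first seen on day 43 and holds on days 85 and 178. Counted from first documentation, DOR is 178 − 43 + 1 = 136 days with all scans, and 43 − 43 + 1 = 1 day under the first two rows. The SAP text starts DOR at first documentation, but its formula starts at confirmed response. If day 85 is the confirming scan, the uncut value is 178 − 85 + 1 = 94 days. The size therefore depends on which start is meant.

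**ORR.** If the response is first seen on day 85 or later, the first two rows leave no responding scan. One patient in a cohort of 25 is 1/25 = 4 percentage points.

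**How many patients.** The documents give no share of incomplete dates. Assume 5 to 20%, and that all 25 patients in a cohort start new therapy: 1.25 to 5 have an incomplete date. In the phase 1b preliminary data (Protocol 4.3.2.2), 75% of treatment discontinuations were for progression. If the remaining 25% carried over to phase 2, 1.25 × 0.25 = 0.3 to 5 × 0.25 = 1.3 patients per cohort would have stopped for another reason. Of these, only patients with a scan between the imputed and true dates that changes BOR or the censoring date are affected.

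**The case against.** The strongest defence is that earliest-date imputation is cautious: in a single-arm trial it avoids crediting the study drug with a response that later therapy produced. Protocol 12.1 also has logic checks and queries for missing and inconsistent dates, and the efficacy analysis is descriptive. All of this lowers the stakes. But a cautious date must still be a possible one, and Appendix B already caps imputed adverse event resolution dates at death and data cutoff, so bounding by known dates is the SAP's own practice.

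A reader might infer more than the documents support:

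- That every incomplete date becomes the day after the last dose. Later-year and most day-only-missing dates do not; they can still precede valid scans, but by less.
- That a scan in the final cycle always follows the imputed date. The 14 to 21 day gap needs the last dose to be in the cycle just before a scan cycle.
- That progression events are lost. Read literally, the PFS and TTP limits, which DOR shares, apply only to patients without documented progression (or death, for PFS and DOR), so a documented progression after the imputed date still counts. A dropped progression scan does not change the ORR numerator either.
- That the EOT visit proves therapy had not started. Protocol 6.3.1 puts EOT before new therapy, but 8.6.4.1 only asks for it 30 to 40 days after the last dose.
- That 1 to 5 patients per cohort are harmed. Under the assumed shares, that counts everyone with an incomplete date.

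**Conclusion.** The point holds in a limited form. Followed exactly, Appendix B can place new therapy before scans that SAP 7.9 says should count. Those scans then drop out of BOR, and hence ORR and DCR. In patients without documented progression (or death, for PFS and DOR), PFS, DOR and TTP are censored earlier. This is a rule giving a wrong result, not a missing detail.

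For an affected patient the effect can be large: PFS censored at 1.41 rather than 5.85 months in the example, or 4 points of ORR in a cohort of 25. Across the trial it is probably small, because harm needs an incomplete date, a scan between the imputed and true dates, and that scan changing BOR or the censoring date. The frequency is unknown. The conclusion assumes that follow-up stops at new therapy as the protocol requires. It does not support a claim that the phase 2 results would be materially biased.

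**What to change.** In SAP Appendix B, impute the earliest date that is consistent with the known date parts, is after the last dose, and is after the last protocol-scheduled tumour assessment (on-treatment or PFS follow-up). Cap it at death or data cutoff. If the known month or year precedes that assessment, keep the known parts and query the site. The date should be strictly later than the assessment because TTP uses assessments before new therapy, whereas PFS also allows the same day. Do not use the EOT visit alone as a bound.

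In the illustrative patient, all three incomplete forms then give 7 Jul 2022, keep 3 of 3 scans and censor PFS at 5.85 months.

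A blanket rule that no imputed date may ever exclude an assessment would go too far, since it could credit responses recorded after another therapy began. The bounded rule carries a smaller version of that risk, so report the current earliest-date rule as a sensitivity analysis. The cost is a sentence or two in Appendix B, a minor programming change and one extra set of outputs.

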Appendix C Description and Operating Characteristics of the BLRM for Dose Escalation

An adaptive BLRM with overdose control principle is used to guide dose escalation decisions and MTD estimation, along with considerations of other emerging safety, clinical, PK, and pharmacodynamic data.

The 2-parameter logistic regression model used is as follows:

$$\text{logit}(\pi_i) = \log(\alpha) + \beta \log\left(\frac{\text{dose}_i}{\text{dose}_{ref}}\right), \alpha > 0, \beta > 0,$$

where π_i is the DLT rate for dose_i , and dose_{ref} is the reference dose. A quantile-based, weakly informative, bivariate normal prior will be used for $\ln(\alpha)$ and $\ln(\beta)$. This prior will be assigned based on pre-study estimates of median DLT at the provisional dose levels as shown in Table 1 (described by Neuenschwander et al. 2008).

Table 1 Prior Median and 95% Credible Interval for DLT Probabilities at Each Dose Level

Dose Level (mg/kg)	Median DLT Rate	95% Credible Interval for DLT Rate
0.1	0.05	(0, 0.90)
0.2	0.10	(0, 0.92)
0.4	0.20	(0, 0.94)
0.75	0.25	(0, 0.95)
1.5	0.30	(0, 0.96)
3	0.45	(0.01, 0.97)
6	0.50	(0.02, 0.98)

DLT: dose-limiting toxicity.

The model will be updated after each group of approximately 3 patients is enrolled in the current dose level. Each subject will participate in only 1 dose cohort. For each dose level, the posterior probability of having DLT rates that fall into the following intervals will be estimated:

- [0,0.16): under-toxicity.
- [0.16, 0.33): target toxicity.
- [0.33, 1.00]: excessive toxicity.

The simulations to evaluate the operating characteristics are based on provisional dose levels (0.1, 0.2, 0.4, 0.75, 1.5, 3, 6 mg/kg), representing the various distributions of toxicity across dose levels, detailed as shown in Table 2.

Table 2 Dose Escalation Simulation Study of the Probability of DLT

Dose Level (mg/kg)	True P(DLT) at each scenario					
	1	2	3	4	5	6
0.1	0.001	0.01	0.05	0.10	0.25	0.50
0.2	0.02	0.05	0.10	0.20	0.45	0.60
0.4	0.04	0.10	0.20	0.30	0.52	0.70
0.75	0.06	0.20	0.25	0.45	0.60	0.75
1.5	0.08	0.23	0.30	0.55	0.70	0.85
3	0.10	0.26	0.45	0.65	0.80	0.90
6	0.12	0.30	0.50	0.75	0.90	0.99

DLT: dose-limiting toxicity.

The trend of the dose-DLT relationship becomes steeper and MTD is reached earlier from Scenario 1 to Scenario 6. Table 3 shows the operating characteristic results.

Table 3 Operating Characteristics for BLRM Dose Escalation Rule

Scenario	Probability of Recommending a:			Average Proportion of Patients Receiving a:			Average Number of Patients	
	Low Dose	Target Dose		Low Dose	Target Dose		Per study	Experiencing DLT per study
		High Dose	High Dose		High Dose	High Dose		
1	100.0	NA	NA	100.0	NA	NA	24.2	1.5
2	16.2	83.8	NA	47.2	52.8	NA	21.4	3.4
3 ^a	16.1	75.7	6.5	38.7	53.5	7.8	18.9	3.8
4 ^b	12.8	70.3	11.4	28.5	53.8	17.6	16.1	3.9
5 ^c	NA	42.0	16.1	NA	61.7	38.3	10.6	3.7
6 ^d	NA	NA	10.2	NA	NA	100.0	5.9	3.0

BLRM: Bayesian Logistic Regression Model; DLT: dose-limiting toxicity.

Low dose = true DLT rate is [0, 0.16]; target dose = true DLT rate is [0.16, 0.33]; high dose = true DLT rate is [0.33, 1.00].

a Probability of 1.7% to claim all doses are toxic.

b Probability of 5.5% to claim all doses are toxic.

c Probability of 41.9% to claim all doses are toxic.

d Probability of 89.8% to claim all doses are toxic.

In Scenario 1 where all true DLT rates are below 0.33, the average number of patients required is approximately 24 with 1.5 DLTs expected on average.

The true DLT rates in Scenario 2 increase faster than Scenario 1 but are still all below 0.33, and the BLRM has an 83.8% chance of successfully recommending target dose levels. The average number of patients required is approximately 21, with 3.4 DLTs expected on average.

In Scenario 3, there is a 16.1% chance of recommending a lower dose as MTD and a 75.7% chance of successfully recommending target dose levels. The average number of patients required is approximately 19, with 3.8 DLTs expected on average.

In Scenario 4, with a faster increase of DLT rate over doses, there is 70.3% chance of claiming the target doses as MTD, an 11.4% chance of recommending a toxic dose, and approximately a 5.5% chance of claiming all doses are toxic. The average number of patients required is approximately 16 with 3.9 DLTs expected on average.

Scenario 5 further increases the DLT rate over dose levels and has a 42.0% chance of recommending a target dose level as MTD, a 16.1% chance of recommending a toxic dose, and a 41.9% chance of claiming all doses as toxic. This scenario requires, on average, approximately 11 patients, and results in 3.7 DLTs on average.

When all doses are toxic, as in Scenario 6, there is an 89.8% chance of successfully claiming all doses are toxic. The average number of patients required is approximately 6 and 3.0 DLTs are expected on average.

The accuracy of the BLRM recommendation relies on the true DLT rate; thus, the safety, clinical, PK, and pharmacodynamic data evaluation are combined to support the dose escalation. As an example, a hypothetical dose escalation is shown in Table 4 to illustrate how BLRM guides dose escalation.

Table 4 Hypothetical Dose Escalation Steps

Step	Dose (mg/kg)	#patients	#DLTs	Next Recommended Dose (mg/kg)
1	0.1	3	0	0.2
	0.1	3	0	
2	0.2	3	1	0.4
	0.1	3	0	
3	0.2	3	1	1.5
	0.4	3	0	
	0.1	3	0	
4	0.2	3	1	0.4
	0.4	3	0	
	0.75	3	2	
	0.1	3	0	
5	0.2	3	1	0.2
	0.4	6	2	
	0.75	3	2	
	0.1	3	0	
6	0.2	6	1	0.2 mg/kg is claimed as the MTD
	0.4	6	2	
	0.75	3	2	
	0.1	3	0	

DLT: dose-limiting toxicity; MTD: maximum tolerated dose.

In addition, the BLRM is flexible in handling late-onset toxicities and can be fed with events meeting DLT criteria but occurring in later cycles to modulate dose escalation, as needed.
